6.2.2.5 Assessing Effect Modification

Estimation of effect modification of the adjusted hazard ratios will be conducted for secondary objectives 28, 29, 31. The crude and adjusted hazard ratios will be estimated as described in Sections 4.1.4 and 4.1.6 within each level of the potential effect modifier. Due to the expected sparse outcomes and the data source restriction on IUD type, these analysis will be conducted only using the pooled data, not by data source.

For objective 28, the Cox model will include breastfeeding status, early (≤ 14 weeks) versus late (> 14 weeks) postpartum status, and their interaction. The P value of the type 3 group test for interaction will be reported. The hazard ratio for breastfeeding status (yes vs. no) will be reported within each level of early (≤ 14 weeks) and late (> 14 weeks) postpartum status. The hazard ratio for postpartum status (≤ 14 weeks vs. > 14 weeks) will be reported within each level of breastfeeding status. In addition, for reporting purposes, the group of no breastfeeding and > 14 weeks postpartum will be considered the referent, and hazard ratios will be reported for postpartum period ≤ 14 weeks and breastfeeding, ≤ 14 weeks and no breastfeeding, and > 14 weeks and breastfeeding. The adjusted hazard ratio will be obtained using the weighted Cox model. One propensity score model using these four (2×2) categories as the dependent variable will be developed. Balance on baseline covariates among the four categories in the weighted sample will be assessed.

For objectives 29 and 31, the Cox models will include the exposure of interest (breastfeeding status or postpartum categories), IUD type, and the interaction between exposure and IUD type. The P value of the type 3 group test for interaction will be reported. The hazard ratio for the exposure of interest will be reported within each level of IUD type. The adjusted hazard ratio will be obtained using the weighted Cox model. The weights will be estimated using the same propensity score models developed for the exposure-outcome pairing (Section 9.3).

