4.8 Study size

Uterine perforation is an uncommon event; 1.3 cases per 1,000 IUD insertions were reported in the EURAS-IUD at 1-year follow-up (Heinemann et al., 2015). The EURAS-IUD also showed that the incidence was higher in breastfeeding women and with early (≤ 36 weeks) postpartum insertion.

Based on results from the validation/feasibility study, the expected number of women with insertion of an IUD available through 30 June 2018, from the four health care systems is approximately $N = 225,000$, with breastfeeding status available for approximately 60,000 of the total. For the two primary objectives related to the risk of uterine perforation, the power of the study is based on detecting a difference in the estimated risk of uterine perforation with respect to (1) breastfeeding status at the time of IUD insertion and (2) time of IUD insertion after pregnancy delivery. The null hypothesis is no difference in risk of perforation by breastfeeding or time of IUD insertion. There will be no adjustment for multiplicity.

For a two-sided test of the hazard ratio (Schoenfeld, 1983), based on a perforation risk of 1.3 per 1,000 insertions in the 1 year after insertion, a hazard ratio of 2.0 can be detected at the two-sided $\alpha = 0.05$ significance level with the following power:

- 85% for breastfeeding versus not breastfeeding (assuming 60% of women with available breastfeeding status are breastfeeding)
- 73% for ≤ 6 weeks, > 99% for > 6 and ≤ 14 weeks, and 73% for > 14 and ≤ 52 weeks versus > 52 weeks postpartum IUD insertion (assuming a postpartum period allocation of 5:20:5:70)

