There were approximately 325,000 IUD insertions identified during the time frame of the validation/feasibility study (i.e., end date, 30 September 2015), and approximately 65% of those occurred after at least 12 months within the data source. In approximately 90% of IUD insertions, this was the first observed insertion for each woman. Approximately 30% of women were identified as having an IUD inserted within the first 52 weeks postpartum. Based on these results and assumptions—approximately three additional years of data more than the validation study and allowing for a loss of approximately 15% of the insertions due to missing data and the propensity score trimming process (Section 9.7.1.3.2)—the number of first insertions of an IUD available through June 2018 from the four health care systems is anticipated to be approximately 225,000, with breastfeeding status available for approximately 60,000. For the two primary objectives related to the risk of uterine perforation, the power of the study is calculated for differences in the estimated risk of uterine perforation with respect to (1) breastfeeding status at the time of IUD insertion and (2) time interval of the IUD insertion following delivery. The null hypothesis to be tested for primary objective 1 is that the natural logarithm of the adjusted summary perforation hazard ratio for breastfeeding versus not breastfeeding at the time of IUD insertion is equal to 0. Using information from validation study, the expected allocation ratio of breastfeeding versus not breastfeeding is 60:40 for this objective. Three null hypotheses to be tested for primary objective 2 are that the natural logarithm of the adjusted summary perforation hazard ratio for early (i.e., ≤ 6 weeks postpartum, > 6 and ≤ 14 weeks, > 14 and < 52 weeks) versus later (i.e., > 52 weeks) postpartum IUD insertion is equal to 0. Based on information from the validation study, the expected allocation ratio of the corresponding postpartum period categories is 5:20:5:70 for this objective.

Power calculations for the expected number of IUD insertions were performed using PASS 14 software (NCSS, LLC, Kaysville, Utah) for a two-sided test of the hazard ratio (Schoenfeld, 1983). Table 4 indicates the power to detect various hazard ratios at the two-sided $\alpha = 0.05$ significance

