level based on a perforation risk of 1.3 per 1,000 insertions and the percentage of insertions expected for the exposure groups of interest, i.e., breastfeeding versus not breastfeeding and early versus late postpartum insertion for the two cutpoints of interest.

Table 4. Power to detect hazard ratio for uterine perforation based on anticipated number of intrauterine device insertions and exposure group allocation

Exposure groups	Number of insertions expected	Allocation % (exposed: unexposed)	Hazard ratio that can be detected (% power)				
			1.5	1.75	2.0	2.25	2.5
Primary objective, 1: Breastfeeding vs. not breastfeeding	60,000	60:40	42	68	85	94	98
Primary objective, 2: Categories of postpartum insertion timing: ≤ 6 weeks vs. > 52 weeks, including women without a recorded delivery within the past 52 weeks	168,750	5:70	32	54	73	85	92
Primary objective, 2: Categories of postpartum insertion timing: > 6 and ≤ 14 weeks vs. > 52 weeks, including women without a recorded delivery within the past 52 weeks	202,500	20:70	78	97	> 99	> 99	> 99
Primary objective, 2: Categories of postpartum insertion timing: > 14 weeks and ≤ 52 weeks vs. > 52 weeks, including women without a recorded delivery within the past 52 weeks	168,750	5:70	32	54	73	85	92

Table 5 displays the power to detect various hazard ratios at the two-sided $\alpha = 0.05$ significance level for the risk of perforation among LNG-releasing versus copper IUDs based on a perforation risk of 1.3 per 1,000 insertions and the percentage of insertions expected for the exposure groups of interest, i.e., timing of postpartum insertion and breastfeeding versus not breastfeeding.*

* These numbers are provided per the FDA request in the letter of 18 May 2016 to address the request to account for “sufficient number of users of both types of IUDs to allow secondary analyses of the comparative safety of LNG IUSs vs. copper IUDs with regard to early postpartum insertion and breastfeeding status at the time of insertion.” These power calculations are not necessarily directly linked to objectives, but rather indicate that adequate data are likely to be available to characterize comparative safety of LNG IUSs and copper IUDs.

Table 5. Power to detect hazard ratio for uterine perforation for LNG versus copper IUDs based on anticipated number of intrauterine device insertions and an 80% (LNG) versus 20% (copper) exposure group allocation

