Covariates will be assessed for inclusion in propensity score models based on association with the study outcome (Brookhart et al., 2006) and thus will not be outcome blinded. Categorical variables will be assessed for inclusion based on indicator coding of the categories. Continuous variables (including integer count variables) will be assessed for inclusion as continuous, dichotomous, and categorical (i.e., indicator coded) variables, as appropriate. Covariates will be included in the propensity score model if the crude hazard ratio is greater than 1.11 or less than 0.90. Additional confounders will be selected for inclusion within propensity score models if a 10% change in the hazard ratio of the *exposure*-outcome relationship occurs when adjusting for that variable, including a 10% change in any level of a categorical exposure variable.

From the fitted logistic regression models, propensity scores will be estimated for each IUD insertion. The distribution of propensity scores among categories (e.g., breastfeeding at the time of IUD insertion versus not breastfeeding at the time of IUD insertion) will be examined.

The propensity scores will be used to calculate weights for each IUD insertion within each exposure group. The weights will be the “overlap weights” and will use data from the IUD insertions included in the propensity score models after reweighting (Li et al., 2018).^{*} To assess whether covariates are balanced across exposure groups after weighting, the distribution of each variable will be compared between categories of the exposure variable, and balance parameters (e.g., standardized differences) (Austin and Stuart, 2015) will be calculated. Pairwise balance parameters (e.g., pairwise standardized differences) will be used for the categorical exposure variable (postpartum timing) in which each category will be compared to the referent group. The balance between exposure groups will be assessed overall and within each data source. If the groups are unbalanced on key covariates after application of overlap weighting, then the logistic regression model will be revised by

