4.1.5 Confounder or Bias Adjusted Analyses

Confounding will be controlled through the use of propensity scores, based on the values of covariates at the time of IUD insertion. The propensity score estimates the probability that a given patient will be exposed conditional on measured covariates and can serve as a summary confounder variable. Propensity scores can perform better than conventional regression methods when the number of events relative to the number of potential confounders is small, because rather than having to model the events with many variables, which may lead to overfitting of the outcome model, one can instead model the exposure, for which the larger number of exposed people provides sufficient data to accommodate a rich model (Cepeda et al., 2003). This advantage may be important in this study, given the low number of expected events, particularly for uterine perforation, within this study.

The steps in estimating adjusted exposure effects are listed as follows:

1. Derive variables that will be considered for inclusion in the propensity score models.
2. Assess balance between exposure groups in the sample.
3. Identify key variables to be included in the propensity score model.
4. Estimate propensity scores and assess the overlapping area among all exposure groups.
5. Calculate weights, normalize the weights, and examine the normalized weights.
6. Assess balance between exposure groups in the weighted sample.
7. Add to the propensity score model additional terms (e.g., interaction or higher order terms) of the covariates that do not balance.
8. Fit the new propensity score model and estimate the propensity scores.
9. Repeat steps 5-8 until all the key covariates are balanced.
10. Estimate the exposure effect that accounted for the confounders via weighting.

Propensity scores for exposure variables will be estimated by fitting a logistic regression model (for dichotomous exposure variables) or a multinomial logistic regression model (for exposure variables with more than two categories). The dependent variable in the propensity score model is exposure status (e.g., women breastfeeding at the time of IUD insertion vs. not breastfeeding at the time of IUD insertion).

Breastfeeding status, postpartum timing, and IUD type will be included within the propensity score model (as independent variables when not the dependent variable). Other covariates will be assessed

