Concomitant gynecological procedure	Indicator variable: 1 = Yes if any of the following procedures occurred on the index date: abortion, aspiration and curettage, dilation and curettage, excision/biopsy of cervix or uterus, ablation, colposcopy and other cervical procedures, hysteroscopy, laminaria, laparoscopy, lysis adhesions, myomectomy, nerve procedure, salpingectomy/oophorectomy 0 = No if none of the above procedures occurred on the index date
Exposures	
Postpartum number of days	Number of person-days, starting on the most recent pregnancy delivery date prior to or on the index date and ending on the index date . There will be a derived postpartum number of days associated with each insertion for each woman. This variable will range from 0 to 365 days and will be missing if the most recent pregnancy delivery date is not recorded or is more than 365 days before the index date .
Postpartum—14-week, dichotomous	Indicator variable: * If postpartum number of days ≤ 98, then postpartum—14-week, dichotomous = 1 * If postpartum number of days > 98 or missing, then postpartum—14-week, dichotomous = 0

Variable	Definition ^a
Postpartum—36-week, dichotomous	Indicator variable: * If postpartum number of days ≤ 252 , then postpartum—36-week, dichotomous = 1 * If postpartum number of days > 252 or missing, then postpartum—36-week, dichotomous = 0
Postpartum—categorical	Categorical variable: * If postpartum number of days ≤ 42 , then postpartum—categorical = 1 (6 weeks or less) * If postpartum number of days > 42 and ≤ 98 , then postpartum—categorical = 2 (> 6 to ≤ 14 weeks) * If postpartum number of days > 98 and ≤ 365 , then postpartum—categorical = 3 (> 14 to ≤ 52 weeks) * If postpartum number of days > 365 or missing, then postpartum—categorical = 0 (> 52 weeks or no delivery)
Outcomes	
Person-time at risk (days, i.e., time to event/censor)	Number of person-days, starting on the index date of IUD insertion and ending on the earliest of date uterine perforation confirmed , date IUD expulsion confirmed , or censoring date . A derived number for person-time at risk will be associated with each IUD insertion for each woman.
Uterine perforation event indicator	Indicator variable: 0 = No date of uterine perforation confirmed during the person-time at risk 1 = Yes, date of uterine perforation confirmed during the person-time at risk

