9.3 Propensity Score Models Defined by Exposure and Outcomes of Interest

Model Number	Exposure (Dependent Variable of Propensity Score Model)	Outcome (Not Included in Propensity Score Model)	IUD Insertion	Covariate Selection	Objective Number
1	Breastfeeding status (yes vs. no)	Uterine perforation	First insertion	Yes	1 (primary objective) 29
2	Postpartum insertion (4 categories)	Uterine perforation	First insertion	Yes	2 (primary objective) 14 ^a 15 ^a 17 ^a 31
3	IUD type (LNG vs. copper)	Uterine perforation	First insertion	Yes	16
4	Menorrhagia (yes vs. no)	Uterine perforation	First insertion	Yes	19
5	Breastfeeding status (yes vs. no)	IUD expulsion	First insertion	Yes	20 30
6	Postpartum insertion (4 categories)	IUD expulsion	First insertion	Yes	23 21 ^a 22 ^a 25 ^a 32
7	IUD type (LNG vs. copper)	IUD expulsion	First insertion	Yes	24
8	Menorrhagia (yes vs. no)	IUD expulsion	First insertion	Yes	27
9	Interaction of breastfeeding and early vs. late postpartum (breastfeeding/ \leq 14 weeks; breastfeeding/ $>$ 14 weeks; no breastfeeding/ \leq 14 weeks; no breastfeeding/ $>$ 14 weeks [referent])	Uterine perforation	First insertion	Yes	28
10	Breastfeeding status (yes vs. no)	Uterine perforation	Subsequent insertions	No ^b	18
11	Postpartum insertion (4 categories)	Uterine perforation	Subsequent insertions	No ^b	18 ^a
12	IUD type (LNG vs. copper)	Uterine perforation	Subsequent insertions	No ^b	18
13	Breastfeeding status	IUD expulsion	Subsequent insertions	No ^b	26
14	Postpartum insertion (4 categories)	IUD expulsion	Subsequent insertions	No ^b	26 ^a
15	IUD type (LNG vs. copper)	IUD expulsion	Subsequent insertions	No ^b	26

IUD = intrauterine device; LNG = levonorgestrel.

- ^a Secondary objectives include dichotomization of “early” and “late” postpartum categories. Separate propensity score models will not be *developed* for these objectives. Rather, the propensity scores calculated with the four-category variable will be used. The propensity scores for dichotomous exposure groups will be calculated by collapsing multiple categories (e.g., propensity score for ≤ 14 weeks = propensity score for ≤ 6 weeks + propensity score for > 6 to ≤ 14 weeks).

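### Objective 28 reports breastfeeding hazard ratios within two postpartum bands without controlling days since delivery inside each band; for objective 1 the scale of the timing covariate is not stated

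*SAP*

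**What the plan says.** **Objective 28.** SAP 6.2.2.5 fits a weighted Cox model with breastfeeding, postpartum status (≤ 14 vs > 14 weeks) and their interaction. "The hazard ratio for breastfeeding status (yes vs. no) will be reported within each level of early" and late postpartum status, the timing HR is reported within each breastfeeding level, and an interaction P value is given. The weights come from model 9 in SAP 9.3, whose dependent variable is the four-group cross described as "Interaction of breastfeeding and early vs. late postpartum". Balance is to be checked on baseline covariates among those four groups. The population is Analysis Set 2 (SAP 5.1.2), so the late stratum ends at 52 weeks.

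**Objective 1.** SAP 4.1.5 states: "Breastfeeding status, postpartum timing, and IUD type will be included within the propensity score model (as independent variables when not the dependent variable". It does not say whether timing enters as bands or as days. Protocol 9.7.1.3.2 uses the same term "for the categorical exposure variable (postpartum timing", when describing balance checks with timing as the exposure. SAP 4.1.5 also draws candidate covariates from Sections 3 and 4.6 and allows continuous forms.

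**Days are available.** SAP 4.6, Table 1, derives postpartum number of days, 0 to 365, for each insertion ("Number of person-days, starting on the most recent" delivery date). The table lists it under exposures, not under baseline covariates.

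**The concern.** Time since delivery is the other exposure under study, and it may be related to both breastfeeding and perforation. In model 9 it is part of what is predicted, so the weights cannot balance it within a band. The Cox model separates women only at week 14, which also drops the 6-week cut used in objective 2. A planned balance check limited to baseline covariates would not reveal an imbalance in days.

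Suppose breastfeeding women in the late stratum tend to have had earlier insertions, and earlier insertion carries higher risk. Part of the timing effect would then be reported as a breastfeeding effect. Unequal bias in the two strata would distort their ratio, which is the effect modification that objective 28 sets out to measure.

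For objective 1 the question is narrower. It is a primary hypothesis, the analysts are not blinded to outcome, and the form of a mandatory covariate is left open.

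**Working it through.** **1. The plan's own figure.** Protocol 4.8 says "a hazard ratio of 2.0 can be detected at the two-sided" 0.05 level, with 85% power for objective 1. Protocol 9.5 gives the method ("for a two-sided test of the hazard ratio (Schoenfeld, 1983") and the rate ("level based on a perforation risk of 1.3 per 1,000 insertions"). Expected events: 60,000 × 0.0013 = 78. With 60:40 allocation, power = Φ(√(78 × 0.6 × 0.4) × ln 2 − 1.96) = 0.851, which matches. The other cells in that row of Table 4 (42, 68, 94 and 98%) also match. The scale chosen for timing does not change this figure. The documents state no figure for bias, so the rest rests on assumptions.

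**2. Mechanism, by hand.** Set the true breastfeeding HR to 1 and split the late band at week 36, with half the insertions on each side. Let breastfeeding be 0.50 before and 0.25 after, and let risk before be 2.3 times risk after.

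- Mean relative risk, breastfeeding: (0.5×0.50×2.3 + 0.5×0.25) / 0.375 = 1.867
- Mean relative risk, not breastfeeding: (0.5×0.50×2.3 + 0.5×0.75) / 0.625 = 1.520
- Apparent HR: 1.867 / 1.520 = 1.23. With a gradient of 1.2 instead of 2.3 it is 1.133 / 1.080 = 1.05.

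**3. Range for the late stratum.** Inputs from the plan: band shares 5:20:5 (Protocol 9.5). Assumptions: insertions uniform within each band; breastfeeding 0.6 at week 14, moving on a logistic curve; risk gradient either a step at week 36 or log-linear at the stated ratio per 26 weeks. True HR is 1.0. Each cell shows step / log-linear.

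| Breastfeeding at week 52 | Gradient 1.2 | Gradient 1.5 | Gradient 2.3 |
|---|---|---|---|
| 0.40 | 1.02 / 1.02 | 1.04 / 1.04 | 1.08 / 1.08 |
| 0.28 | 1.03 / 1.03 | 1.06 / 1.07 | 1.13 / 1.14 |
| 0.15 | 1.04 / 1.05 | 1.10 / 1.10 | 1.19 / 1.22 |
| 0.04 | 1.07 / 1.07 | 1.14 / 1.16 | 1.29 / 1.34 |

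The top value, 1.34, needs the steep log-linear form, which amounts to 2.3^(38/26) = 3.4-fold over the whole 38-week band. If the total fall is limited to 2.3-fold, the maximum is 1.29.

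**4. Early stratum.** The same curves give 1.00-1.04. A direct calculation pooling ≤ 6 and > 6 to 14 weeks at 5:20, with breastfeeding 0.40-0.80 in the first part and 0.55-0.65 in the second and a risk ratio of 0.5-3 between them, gives 0.79-1.28. The direction there is not determined.

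**5. Effect on the interaction test.** If risk is equal across bands, the 78 events split into 78 × 25/30 = 65 early and 78 × 5/30 = 13 late. With 60:40 by breastfeeding in the early band and an even split in the late band, the standard error of the log ratio of HRs is √(1/39 + 1/26 + 1/6.5 + 1/6.5) = 0.61. A false ratio of 1.2 is rejected in 6.0% of studies and 1.3 in about 7%, instead of 5%. With three times the events these become 8.1% and 11.6%.

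**6. Objective 1.** With three-band adjustment and overlap weights, the curves in step 3 leave an apparent HR of 1.00-1.04. At 78 events, a bias of 1.03 gives 5.2% rejection instead of 5%.

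**The case against.** The strongest reply is that the documents contain no gradient inside weeks 14-52. The 2.3-fold figure in Protocol Table 2 compares all insertions up to 36 weeks with all later ones, without upper limit, and its interval is 1.1-4.7. Protocol 9.5 puts about 20% of that cohort in the early group, so the later group is mostly an unbounded remainder. No passage gives breastfeeding by week either. This stands, and it is why the gradient is varied from 1.2 to 2.3 and the result given as a range.

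Objective 28 is also secondary, the two-category timing was an FDA request (Protocol section 5), and hypothesis testing is planned for the primary objectives only. With a standard error of 0.61, the interval for the ratio spans a factor of about 3.3 each way. That limits the practical effect on the interaction test. It does not justify leaving an adjusted within-band HR uncontrolled for a variable already in the dataset.

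A remedy can also cost more than it appears to. A full spline in the Cox model is heavy for 13 late events. Separate weights in each band cannot supply the early-versus-late or common-referent HRs that Table Layout 11 requires. Both points stand and shape the fix.

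A reader might infer that primary objective 1 is adjusted only in wide bands and is therefore materially biased. The SAP leaves the scale open, days are not excluded, and the computed bias is small even if bands are used. A reader might also infer that every error pushes the breastfeeding HR upward; the early-stratum result does not support that.

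**Conclusion.** The omission in objective 28 is real: no planned step controls, or checks, days since delivery within either band. Whether it biases the result depends on breastfeeding and risk both varying with time inside a band, and the documents do not show this. Under the stated assumptions a null effect would appear as about 1.02-1.34 in the late stratum. The early-stratum bias could go either way, so the direction of a false interaction is not fixed. The main concern is the distorted late-stratum HR; at the planned event count the rise in false rejections is modest.

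For objective 1 the defect is an unstated scale, with residual bias of about 1.00-1.04 if bands are used. It should be settled in advance because settling it is easy, not because the primary conclusion is at risk.

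**What to change.** (a) In propensity models 1 and 5, enter postpartum number of days in a flexible form, such as a spline, alongside the bands. Models 10 and 13 need no separate change, since SAP 9.3 carries first-insertion terms over to them.

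(b) For objective 28, keep model 9 for the early-versus-late and common-referent HRs. Estimate the within-band breastfeeding HRs and their ratio in one of two ways: with breastfeeding overlap weights fitted separately in each band with days as a covariate, or by adding one low-order days term, centred within band, to the weighted Cox model. Do not add raw days to model 9: days determine the band, so the groups would not overlap.

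(c) Report the standardized difference in days by breastfeeding status within each band, before and after weighting.

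Cost: no new data. Under (b), either one additional set of weights with a slightly different target population in each band, or one or two extra outcome-model parameters.
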